5. ANALYSIS SETS

Analysis sets are described in the Master COV-01 SAP.

Additional analysis sets that are specific to sub-protocol COV-01-005 are described below.

5.1. PHARMACOKINETIC ANALYSIS SET

The pharmacokinetic (PK) analysis set will include patients from the safety analysis set (refer to Master COV-01 SAP Section 5.2) who were randomized to the zilucoplan plus SoC treatment arm and had at least one measured post-baseline concentration (refer to Master COV-01 SAP Section 6.2 for baseline definition).

5.2. PHARMACODYNAMIC ANALYSIS SET

[figure not shown]
The pharmacodynamic (PD) analysis set will include patients from the safety analysis set (refer to Master COV-01 SAP Section 5.2) who were randomized to COV-01-005 sub-protocol and had at least one measured biomarker (e.g., C5, etc.).

5.3. ANTI-DRUG ANTIBODY ANALYSIS SET

The anti-drug antibody (ADA) analysis set will include patients from the safety analysis set (refer to Master COV-01 SAP Section 5.2) who were randomized to COV-01-005 sub-protocol and had at least one evaluated ADA sample (negative or positive).

5.4. PROCESS FOR ANALYSIS SET ASSIGNMENT

As the PK, PD, and ADA analysis sets are defined based on objective criteria only, the authorization of this sub-protocol SAP will stand for the agreement and authorization of the inclusion/exclusion of each patient in these PK, PD, and ADA analysis sets.

6. GENERAL CONSIDERATIONS

Details are provided in the Master COV-01 SAP.

7. STATISTICAL CONSIDERATIONS

7.1. SAMPLE SIZE CALCULATION

Details are defined in the Master COV-01 SAP.

7.2. MISSING DATA

Details are defined in the Master COV-01 SAP.

7.3. STATISTICAL TESTS

Not applicable since no statistical inferences will be performed for the final analysis of this sub-protocol (refer to Section 16).

7.4. MULTIPLE COMPARISONS/MULTIPLICITY

Not applicable since no statistical inferences will be performed for the final analysis of this sub-protocol (refer to Section 16).

7.5. MULTICENTER STUDY

Details are defined in the Master COV-01 SAP.

7.6. ADJUSTMENTS FOR COVARIATES AND FACTORS TO BE INCLUDED IN ANALYSES

Not applicable since no statistical inferences will be performed for the final analysis of this sub-protocol (refer to Section 16).

7.7. EXAMINATION OF SUBGROUPS

No subgroup analyses will be performed for the final analysis of this sub-protocol (refer to Section 16).

7.8. SOFTWARE VERSION

Details are defined in the Master COV-01 SAP.

8. OUTPUT PRESENTATIONS

Output presentations are described in the Master COV-01 SAP.

9. DISPOSITION AND WITHDRAWALS

Analysis of disposition and withdrawals will be presented as described in the Master COV-01 SAP.

10. DEMOGRAPHIC AND OTHER BASELINE CHARACTERISTICS

Demographic characteristics and other baseline characteristics data will be presented as described in the Master COV-01 SAP.

11. DISEASE HISTORY

[figure not shown]
Analysis of disease history at screening will be performed as described in the Master COV-01 SAP.

CCI

PPD

Version Number: Amendment 2, v1.0
Version Date: 28-Jul-2021

CCI

12. MEDICAL HISTORY

Analysis of medical history will be performed as described in the Master COV-01 SAP.

13. PRIOR AND CONCOMITANT MEDICATIONS

In addition to the analysis of prior and concomitant medications described in the Master COV-01 SAP, antibiotic prophylaxis, collected on the *Antibiotic Prophylaxis* page of the electronic Case Report Form (eCRF), will also be coded to the World Health Organization (WHO) Drug Global dictionary, version B3 March 2020 (or later).

Concomitant use (refer to Master COV-01 SAP Section 13 for definition of concomitant use) of antibiotic for any indication as well as of antibiotic prophylaxis for Neisseria infection will be summarized separately by Anatomical Therapeutic Class (ATC) level 2, preferred drug name, and treatment arm based on the FAS (refer to Master COV-01 SAP Section 5.1). Separate summary of patients randomized to COV-01-005 placebo plus SoC treatment group will be provided. A patient having more than one medication within the same ATC level 2 or preferred drug name will be counted only once for that ATC level 2 or preferred drug name.

Furthermore, duration of concomitant use of antibiotic for any indication (days) and number and percentage of patients who received antibiotic prophylaxis for Neisseria infections concurrently while receiving the study drug and up to 14 days after the last dose of the study drug will be presented by treatment arm based on the FAS. Separate summary of patients randomized to COV-01-005 placebo plus SoC treatment group will be provided.

All antibiotic prophylaxis will be listed.

13.1. DERIVATION

Duration of concomitant use of antibiotic for any indication, in days, will be derived as follows:

- Duration of concomitant use of antibiotic for any indication (days) = {[Date of latest stop date of any antibiotic received on or after the first dose of study drug – Latest of (date of earliest start date of antibiotic received on or after the first dose of study drug, date of first dose of study drug)] + 1} – [sum of any gap (days) in concomitant use of antibiotics for any indication on or after the first dose of study drug]

14. EXPOSURE TO STUDY DRUG

Patients randomized to sub-protocol COV-01-005

Patients randomized to zilucoplan plus standard of care (SoC) and placebo plus SoC treatment arms of COV-01-005 sub-protocol will receive a single daily dose of 32.4 mg of the study drug (prefilled syringes containing 0.81 mL of zilucoplan or placebo, as appropriate) administered by subcutaneous (SC) injection in the abdomen (preferred site), thigh or upper arm.

The daily administration of study treatment will start on Day 1 (baseline) and continue to Day 14 or until hospital discharge, whichever occurs first. If the patient is discharged before 14 days of treatment, zilucoplan or placebo should be stopped at time of discharge or 24 hours before discharge.

Reason for dose modification of study drug (i.e. dose interrupted or drug withdrawal) will be captured in the *Exposure* page of the eCRF.

Patients included in the control arm of COV-01-005 sub-protocol who were randomized to the placebo plus SoC group of a sub-protocol other than COV-01-005

It is to be noted that the planned duration of exposure to a study drug, planned frequency of administration of the study drug, and planned route of administration of the study drug will vary from one sub-protocol to the other, but similar information as for COV-01-005 sub-protocol will be captured on the *Exposure* page of the eCRF of these other sub-protocols.

Exposure to study drug

The exposure to study drug will be summarized by treatment arm (breaking down the placebo plus SoC arm by sub-protocol) based on the safety analysis set as follows:

[figure not shown]
- Duration of exposure:
 - Duration of exposure (days) as a continuous variable;
 - Duration of exposure (days) as a categorical variable: 1 to 3, > 3 to 7, > 7 to 14, and > 14;
 - Total number of doses received as a continuous variable, where the total number of doses received is defined as the total number of doses received by each patient, not the total number of doses received across all patients.

CCI

PPD

Version Number: Amendment 2, v1.0
Version Date: 28-Jul-2021

CCI

- Dose modifications:
 - Number and percentage of patients with at least one interrupted dose;
 - Number and percentage of patients with at least one dose interruption by reason for dose interruptions:
 - Adverse events;
 - Other.
 - Total number of dose interruptions as a continuous variable, where the total number of dose interruptions is defined similarly to the total number of doses received;
- Number and percentage of patients with at least one overdose.

All dosing and exposure data will also be listed.

14.1. DERIVATIONS

For patients randomized to a study drug planned to be administered on a daily basis, duration of exposure to study drug, in days, will be computed as follows:

- Duration of exposure (days) = (Date of last dose of study drug – Date of first dose of study drug) + 1

For all other patients (i.e. randomized to a study drug planned to be administered not on a daily basis), duration of exposure to study drug, in days, will be computed as follows:

- Duration of exposure (days) = {[Earliest date of (end of planned study treatment period, hospital discharge or discontinuation from study drug)] – Date of first dose of study drug} + 1

15. COMPLIANCE WITH STUDY DRUG

Compliance with study medication will be summarized by treatment arm (breaking down the placebo plus SoC control arm by sub-protocol) based on the safety analysis set. In addition to the descriptive summary, the following compliance categories will be presented:

CCI [Redacted]

- < 80%;
- ≥ 80% to < 100%;
- 100%;
- > 100%.

Compliance data will also be listed.

15.1. DERIVATIONS

For each patient, the compliance will be computed as follows:

- Compliance (%) = (Actual total number of doses / Expected total number of doses) x 100

where:

- Actual total number of doses is defined as the total number of doses (injections) taken (received) through the course of the study;
- Expected total number of doses is defined as the total number of protocol-defined doses (injections) to be taken (received) through the course of the study and is computed as follows:
 - For patients randomized to a study drug administered on a daily basis:
 - Expected total number of doses = Expected number of doses (injections) per day * expected number of days under treatment, where the expected number of days under treatment is defined as: {[Earliest date of (end of planned study treatment period, hospital discharged or discontinuation from study drug)] – Date of first dose of study drug} + 1

- For patients randomized to a study drug planned to be administered not on a daily basis:
 - Expected total number of doses = Expected number of doses (injections) per day * expected number of administration days between randomization and the earliest of (end of planned study treatment period, hospital discharged or discontinuation from study drug)
- For example, if a study drug is planned to be administered once on Day 1 and once on Day 4, the expected total number of doses is 2; unless patient discontinued from study drug or was discharged from the hospital on or after Day 1 but before Day 4, in which case the expected total number of doses is 1. As another example, if the study drug is planned to be administered twice daily on every other day from Day 1 to Day 14, the expected total number of doses is 14; unless patient discontinued from study drug or was discharged from the hospital let say, on Day 10, in which case the expected total number of doses is 10 (i.e., 2 doses [injection] per day * 5 administration days).

16. EFFICACY ENDPOINTS

Given that only 108 patients were randomized into COV-01-005 sub-protocol by the time enrollment into this sub-protocol was terminated early by the Sponsor and that is expected that less than the third of the total number of patients required by the sample size (i.e., ~700; refer to Master SAP Section 7.1) will be included in the final analysis of this sub-protocol, no statistical inferences will be performed for any efficacy endpoint, but two-sided 95% confidence interval (CI) within each treatment arm will be provided, when possible.

In conformance with the FDA's Guidance for Submission of Abbreviated Report and Synopsis in Support of Marking, summary tables will be presented for the primary and key secondary efficacy endpoints (refer to Master SAP Sections 16.1.1, 16.2.1.1, 16.2.1.2, and 16.2.1.3). Although not required by the previously mentioned FDA's Guidance, summary tables will also be provided for the other secondary efficacy endpoints (refer to Master SAP Sections 16.2.1.4 to 16.2.1.9) in order to be compliant with the publication requirements of *ClinicalTrials.gov*. In addition, summary tables will also be provided for the additional efficacy endpoint of incidence of all-cause mortality through Day 60 (refer to Master SAP Section 16.4.1.1).

[figure not shown]
Efficacy summaries will be performed as described in the Master COV-01 SAP.

CCI

PPD

Version Number: Amendment 2, v1.0
Version Date: 28-Jul-2021

CCI

16.1. PRIMARY EFFICACY

16.1.1. TIME TO CONFIRMED CLINICAL RECOVERY THROUGH DAY 29, WITHOUT RE-HOSPITALIZATION THROUGH DAY 29

Details are provided in the Master COV-01 SAP.

16.1.2. MISSING DATA IMPUTATION METHOD FOR PRIMARY EFFICACY ENDPOINT

Details are provided in the Master COV-01 SAP.

16.1.3. MAIN ANALYSIS OF PRIMARY EFFICACY ENDPOINT

For the time to confirmed clinical recovery through Day 29, without re-hospitalization through Day 29, as defined in the Master SAP Section 16.1.1, the number and percentage of patients with and without the event will be presented by randomized treatment arm. Two-sided 95% exact binomial Confidence Interval (CI) will also be provided by treatment arm for the percentage of patients with the event. For patients who did not meet the event, the main reason for censoring will be summarized similarly.

Kaplan-Meier curves (product-limit estimate) will be provided by treatment arm for the time to confirmed clinical recovery through Day 29, without re-hospitalization through Day 29. Kaplan-Meier estimate of the time to confirmed clinical recovery through Day 29, without re-hospitalization through Day 29, in days, will be provided at the 25th, 50th (median), and 75th percentiles time along with their corresponding two-sided 95% CIs. The estimates of the SEs will be computed using the Greenwood's formula, the CI for the median will be calculated according to Brookmeyer and Crowley (1982), and the CIs for the survival function estimates at above mentioned time points will be derived from the Kaplan-Meier estimates using the log-log transformation. Kaplan-Meier estimates of the probability of having the event will also be provided at Day 29 along with the number of patients with the event and the number of patients at risk at that time.

16.1.4. SENSITIVITY ANALYSES FOR PRIMARY EFFICACY ENDPOINT

No sensitivity analyses will be performed for this sub-protocol.

16.1.5. SUPPLEMENTARY ANALYSES FOR PRIMARY EFFICACY ENDPOINT

No supplementary analyses will be performed for this sub-protocol.

16.2. SECONDARY EFFICACY**16.2.1. SECONDARY EFFICACY ENDPOINTS**

Details are provided in the Master COV-01 SAP.

16.2.2. MISSING DATA IMPUTATION METHOD FOR SECONDARY EFFICACY ENDPOINTS

Details are provided in the Master COV-01 SAP.

16.2.3. MAIN ANALYSIS OF SECONDARY EFFICACY ENDPOINTS

Details are provided in the Master COV-01 SAP.

16.2.3.1. Binary Endpoints

For the incidence of patients with oxygen-free recovery at Day 29 (refer to Master SAP Section 16.2.1.1), incidence of patients with ≥ 2 -point improvement from baseline or fit for discharge on the ordinal scale at Day 29 (refer to Master SAP Section 16.2.1.2), incidence of all-cause mortality through Day 29 (refer to Master SAP Section 16.2.1.3), incidence of patients with clinical recovery at Days 8, 15 and 29 (refer to Master SAP Section 16.2.1.8), and incidence of patients with sustained clinical recovery as confirmed by Day 60 follow-up (refer to Master SAP Section 16.2.1.9), the number and percentage of patients with and without the event will be provided by treatment arm. Two-sided 95% exact binomial CI will also be provided by treatment arm for the percentage of patients with the event.

For the incidence of all-cause mortality, primary reason of death will also be summarized by treatment arm.

16.2.3.2. Ordinal Endpoints

For the incidence of patients in each category of the 8-point ordinal scale for clinical severity at Days 8, 15, and 29 endpoints (refer to Master SAP Section 16.2.1.4), the number and percentage of patients in each ordinal scale

CCI

PPD

Version Number: Amendment 2, v1.0
Version Date: 28-Jul-2021

CCI

CCI [Redacted]

category will be provided at each specified Day for each treatment arm. The worst post-baseline score on the 8-point ordinal scale for clinical severity from randomization to Day 29 (refer to Master SAP Section 16.2.1.5) and each “number of days” endpoint (refer to Master SAP Sections 16.2.1.6 and 16.2.1.7) will be summarized similarly.

Shift tables from baseline to each post-baseline day up to Day 29 as well as to the worst post-baseline score will also be provided for the 8-point ordinal scale for clinical severity.

16.2.4. SENSITIVITY ANALYSES FOR SECONDARY EFFICACY ENDPOINTS

No sensitivity analyses will be performed for this sub-protocol.

16.2.5. SUPPLEMENTARY ANALYSES FOR SECONDARY EFFICACY ENDPOINTS

For the incidence of all-cause mortality through Day 29 key secondary efficacy endpoint, the time to all-cause mortality through Day 29, in days, associated will be derived as follows:

- Time to all-cause mortality through Day 29 (days) =
(Date of death / Date of censoring - Date of Study Day 1 [refer to Maser SAP Section 6.1]) + 1.

The date of death will be taken from data captured on the *Death Details* page of the eCRF.

For patients who were alive on Day 29, time to all cause-mortality will be censored at Day 29. For patients with an unknown alive status at the time of the analysis due to missing data, time to all-cause mortality will be censored at the latest date on which the patient was known to be alive before or on the data cut-off date of the analysis. The last date the patient was known to be alive will be the latest date collected on any page of the eCRF. For patients who discontinued from the study before the time of the analysis, time to all-cause mortality will be censored at the date of study discontinuation, as captured on the *Disposition* page of the eCRF.

Number and percentage of patients with and without the event will be presented by randomized treatment arm. For patients who did not meet the event, the main reason for censoring will be summarized similarly.

Kaplan-Meier survival curves by treatment arm will be provided. The 25th percentile, 50th percentile (median), and 75th percentile of time to all-cause mortality through Day 29 (days) with the corresponding two-sided 95% CIs based on the Kaplan-Meier survival curves (refer to Master SAP Section 16.2.4) for each treatment arm will also be presented. The estimate of the SEs will be computed using Greenwood’s formula, the CI for the median will be calculated according to Brookmeyer and Crowley (1982) and the other CIs will be derived from the Kaplan-Meier

CCI [Redacted]

estimates using the log-log transformation. Kaplan-Meier estimates of the probability of having the event will also be provided at Day 29 along with the number of patients with the event and the number of patients at risk at that time.

No supplementary analyses will be performed for the any other secondary efficacy endpoints.

16.3. EXPLORATORY EFFICACY

CCI [Redacted]

16.4. ADDITIONAL EFFICACY

16.4.1. ADDITIONAL EFFICACY ENDPOINT

16.4.1.1. Incidence of All-Cause Mortality through Day 60

Details are provided in the Master COV-01 SAP.

16.4.2. MISSING DATA IMPUTATION METHOD FOR ADDITIONAL EFFICACY ENDPOINT

[figure not shown]
Details are provided in the Master COV-01 SAP.

16.4.3. ANALYSIS OF ADDITIONAL EFFICACY ENDPOINT

The number and percentage of patients alive and dead through Day 60 (refer to Section 16.4.1.1) will be provided by treatment arm along with the two-sided 95% exact binomial CI for the percentage of patients dead through Day 60. Primary reason of death will also be summarized by treatment arm.

16.4.4. SENSITIVITY ANALYSES FOR ADDITIONAL EFFICACY ENDPOINT

No sensitivity analyses will be performed for the additional efficacy endpoint.

16.4.5. SUPPLEMENTARY ANALYSES FOR ADDITIONAL EFFICACY ENDPOINT

The time to all-cause death through Day 60, in days, will be derived as follows:

- Time to all-cause mortality through Day 60 (days) =
(Date of death / Date of censoring - Date of Study Day 1 [refer to Maser SAP Section 6.1]) + 1.

The date of death will be taken from data captured on the *Death Details* page of the eCRF.

For patients who were alive or patients with an unknown alive status at the time of the analysis due to missing data, time to all-cause mortality will be censored at the latest date on which the patient was known to be alive before or on Day 60. The last date the patient was known to be alive will be the latest date collected on any page of the eCRF. For patients who discontinued from the study before Day 60, time to all-cause mortality will be censored at the date of study discontinuation, as captured on the *Disposition* page of the eCRF.

Number and percentage of patients with and without the event will be presented by treatment arm. For patients who did not meet the event, the main reason for censoring will be summarized similarly.

Kaplan-Meier survival curves by treatment arm will be provided. The 25th percentile, 50th percentile (median), and 75th percentile of time to all-cause mortality (days) through Day 60 with the corresponding two-sided 95% CIs based on the Kaplan-Meier survival curves for each treatment arm will be presented. The estimate of the SEs will be computed using Greenwood’s formula, the CI for the median will be calculated according to Brookmeyer and Crowley (1982) and the CIs for the survival function estimates at above mentioned time points will be derived from the Kaplan-Meier estimates using the log-log transformation. Kaplan-Meier estimates of the probability of having the event will also be provided at Day 60 along with the number of patients with the event and the number of patients at risk at that time.

16.5. INTERIM ANALYSIS

No IAs will be performed for this sub-protocol since the trigger for the first IA was not reached by the time enrollment into this sub-protocol was terminated early by Sponsor (refer to Master SAP Section 16.5).

17. SAFETY ENDPOINTS

In addition to the safety analyses are described in Master COV-01 SAP, the following safety analysis will also be provided based on the safety analysis set (refer to Master SAP Section 5.2).

CCI	[Redacted]		
PPD	[Redacted]	Version Number:	Amendment 2, v1.0
		Version Date:	28-Jul-2021
CCI	[Redacted]		
	[Redacted]		
	[Redacted]		

17.1. ADVERSE EVENTS

17.1.1. ADVERSE EVENTS OF SPECIAL INTEREST

The following are defined as adverse events of special interest (AESIs) for this sub-protocol and will be identified based on pre-defined coded preferred terms (PTs), high-level terms (HLTs, and/or system organ class:

- Anaphylactic reactions (Medical Dictionary for Regulatory Activities [MedDRA] algorithmic approached; refer to [Appendix 1](#));
- Serious anaphylactic reactions (MedDRA algorithmic approached; refer to [Appendix 1](#));
- Hypersensitivity reactions (standardized MedDRA query [SMQ] – narrow scope; refer to [Appendix 2](#));
- Serious hypersensitivity reactions (SMQ – narrow scope; refer to [Appendix 2](#));
- Infections (MedDRA system organ class of ‘Infections and infestations’);
- Serious infections (MedDRA system organ class of ‘Infections and infestations’);
- Neisseria infections (MedDRA high level term [HLT] of ‘Neisseria infections’);
- Serious Neisseria infections (HLT of ‘Neisseria infections’);
- Drug related hepatic disorders (SMQ – comprehensive search; refer to [Appendix 3](#)), excluding the ‘Liver neoplasms, benign (incl. cysts and polyps)’ and ‘Liver neoplasms, malignant and unspecified’ sub-SMQs.

A summary of treatment-emergent (refer to Master COV-01 SAP Section 17.1) AESIs overall and by AESI category and preferred term (PT) will be prepared by treatment arm for patients randomized to COV-01-005 only. Should a patient experience multiple events within an AESI category or PT, the patient will be counted only once for that AESI category or PT. The risk difference of the overall incidence rates of having any treatment-emergent AESI between the treatment arms will be presented along with its two-sided 95% Wald CI. A listing of all AESIs will be provided for patients randomized to COV-01-005 only.

CCI

PPD

Version Number: Amendment 2, v1.0
Version Date: 28-Jul-2021

CCI

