#### **8.4.7 Disease-Related Events and/or Disease-Related Outcomes**

Progression, signs, or symptoms of the disease being studied and clinically significant abnormal laboratory findings or other abnormal safety assessments which are associated with the underlying disease should be reported, as appropriate, as an AE or SAE.

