#### 4.1.1 Adverse Events

##### 4.1.1.1 Adverse Events from Zilucoplan

To date, zilucoplan has shown a favorable safety and good tolerability profile across all studies in healthy participants and patients with gMG, PNH, immune mediated necrotizing myopathy (IMNM), and renal impairment. No major safety risks have been identified to date, with > 100 patient years of exposure and > 40,000 injections administered in clinical trials. A difference in the overall AE profiles was seen among the clinical trials in different populations: few AEs occurred in healthy controls and stable renally impaired patients; the AE profile in PNH reflected the hemolytic anemia characteristic of the underlying disease; and in the gMG population, many AEs were reflective of multiple comorbidities, longstanding use of corticosteroid and immunosuppressive therapies, and the more advanced age of this population.

Although no meningococcal infections have been identified with zilucoplan treatment to date, it is well established that inhibition of complement C5 and the terminal complement pathway increases the susceptibility to infection with encapsulated bacteria, in particular *N. meningitidis*. This risk is also described in the prescribing information for the approved complement C5 inhibitor eculizumab (Soliris® US Package Insert 2017) [13].

Given the increased risk for *N. meningitidis* infection with complement C5 inhibition or deficit, patients who have received zilucoplan in ambulatory clinical trials were required to have documentation of *N. meningitidis* vaccination (and booster if appropriate) prior to treatment initiation. In addition, while on zilucoplan, patients were monitored closely for signs and symptoms of *N. meningitidis* infection, including self-monitoring based on detailed instruction about the signs and symptoms of possible meningococcal infections.

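### Zilucoplan SAP: the infection AESI totals can include COVID-19 worsening, and no planned row counts patients with any non-COVID-19 infection

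*SAP*

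**What the plan says.** COV-01-005 SAP 17.1.1 lists nine AESI categories. Two rest on an entire MedDRA system organ class: "Infections (MedDRA system organ class of ‘Infections and infestations" and its serious counterpart, "Serious infections (MedDRA system organ class of" the same name. Neither carries an exclusion. Two narrower categories, all and serious, cover "Neisseria infections (MedDRA high level term [HLT] of" that name. The hepatic category, "Drug related hepatic disorders (SMQ – comprehensive search", does carry an exclusion: two liver-neoplasm sub-queries are removed.

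For display, a summary of treatment-emergent "AESIs overall and by AESI category and preferred term (PT) will be prepared by treatment arm for patients randomized to COV-01-005 only", and every AESI is listed. One between-arm AESI figure is planned: "The risk difference of the overall incidence rates of having any treatment-emergent AESI between the treatment arms will be presented", with a 95% Wald interval.

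The risk in view is set out in the COV-01-005 sub-protocol. Section 4.1.1.1 says that C5 inhibition "increases the susceptibility to infection with encapsulated bacteria, in particular" N. meningitidis. Section 2.3 says that the association known for C5 inhibitors does not extend to viral infections generally or to coronavirus. It also names encapsulated bacteria other than meningococcus as a target of the antibiotic prophylaxis.

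On reporting, Master Protocol 8.4.7 says that "Progression, signs, or symptoms of the disease being studied and clinically significant abnormal laboratory findings" linked to the underlying disease are to be reported, as appropriate, as an AE or SAE. Master Protocol Appendix 4 prefers a diagnosis to individual symptoms. Master SAP 17.1 treats an AE that starts or worsens after the first dose as treatment-emergent.

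**The concern.** The disease under treatment is itself an infection. If its worsening is recorded under a COVID-19 diagnosis term, it can enter the rows meant to show infection harm. Those rows then mix two things that may move in opposite directions: COVID-19 worsening, which is close to an efficacy outcome, and bacterial infection, the harm that the mechanism predicts. An agent that helps COVID-19 while raising bacterial infections could show no difference in the aggregate, or a favourable one.

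The Neisseria rows do not close the gap, because the sub-protocol's stated risk covers encapsulated bacteria more widely. The preferred-term rows do not close it either. A patient counts once within each term, so a patient with two different infections appears in two rows. Adding rows therefore does not give the number of patients with at least one non-COVID-19 infection.

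**Working it through.** The AESI section states no rate, sample size or power, so there is no figure of the plan's own to reproduce on this point. The check has two parts: whether COVID-19 can enter the rows, and how large the effect could be.

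**1. Can COVID-19 enter the rows?** Four conditions must all hold:
- Worsening after the first dose is reported as an AE. Master Protocol 8.4.7 supports this, as appropriate.
- It is recorded as COVID-19 and not as a symptom or complication. Appendix 4 leans that way.
- It is treatment-emergent. Master SAP 17.1 counts worsening.
- The term sits in the Infections and infestations class. This is an assumption, since the documents do not print the MedDRA hierarchy.

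COVID-19 that is present at baseline and does not worsen is not counted.

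**2. Anchor for an illustration.** Master Protocol 9.1 plans on Day 29 mortality of 15% on placebo and 8.25% on the agent, 350 per arm, 80% power. Reproducing that, with a mean rate of 0.11625:

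[0.0675 x sqrt(350) - 1.96 x sqrt(2 x 0.11625 x 0.88375)] / sqrt(0.15 x 0.85 + 0.0825 x 0.9175) = (1.263 - 0.888) / 0.451 = 0.83, which is 79.7% power. The stated 80% is confirmed.

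These rates serve below as assumed COVID-19 event rates, as if each death appeared as one COVID-19 event in the class.

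**3. Whole-class risk.** Let c be the risk of a counted COVID-19 event and b the risk of a bacterial infection, assumed independent. The risk of any infection is 1 - (1 - c)(1 - b).

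Take b = 5% on placebo and 10% on zilucoplan, a true difference of +5.0 points:

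| COVID-19 events, placebo vs zilucoplan | Any infection, placebo | Any infection, zilucoplan | Difference (points) |
|---|---|---|---|
| 15% vs 15% | 19.25% | 23.50% | +4.25 |
| 15% vs 12% | 19.25% | 20.80% | +1.55 |
| 15% vs 8.25% | 19.25% | 17.43% | -1.8 |
| 30% vs 30% | 33.50% | 37.00% | +3.5 |
| 30% vs 25% | 33.50% | 32.50% | -1.0 |
| 30% vs 20% | 33.50% | 28.00% | -5.5 |
| 40% vs 40% | 43.00% | 46.00% | +3.0 |
| 40% vs 30% | 43.00% | 37.00% | -6.0 |

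The COVID-19 benefit that brings the difference to zero is (1 - c0)(b1 - b0)/(1 - b1), where 0 is placebo and 1 is zilucoplan. For c0 = 15%, 30% and 40% it is 0.85 x 0.05/0.90 = 4.7, 0.70 x 0.05/0.90 = 3.9 and 0.60 x 0.05/0.90 = 3.3 points.

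**4. Largest rise fully hidden at 15% vs 8.25%.** b1 = 1 - 0.85(1 - b0)/0.9175. This gives 1% to 8.3%, 5% to 12.0%, 10% to 16.6% and 15% to 21.2% (unrounded 21.25%), so about 6 to 7 points.

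**5. Precision.** COV-01-005 SAP section 16 gives 108 patients randomized; the arm split is not stated. Assume 54:54 or, as an extreme, 7:1 (108 x 7/8 = 94.5 and 13.5). The 7:1 is borrowed from SAP 4.5.2, where it describes active versus control under the master SAP definition of the control arm. For bacterial infection at 5% vs 12%:
- COVID-19 terms removed: +7.0 points, Wald 95% CI -3.4 to +17.4 at 54:54 and -6.3 to +20.3 at 7:1.
- COVID-19 left in at 15% vs 8.25%: 0.0 points, CI -14.9 to +14.9 and -22.5 to +22.5.

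**The case against.** The strongest reply is that the plan already shows most of what is needed. AESIs are tabulated by preferred term and listed, and Master SAP 17.1.1 and 17.1.3 tabulate all and serious treatment-emergent events by class and term. COVID-19 terms and individual bacterial terms would therefore be visible separately. The organism singled out by name, N. meningitidis, has its own all and serious rows, which COVID-19 cannot enter. All of this stands. It narrows the gap to the missing aggregate: a patient count for non-COVID-19 infection, which a reader could only rebuild from the listing patient by patient.

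Second, the plan computes no risk difference for infections. The only one is for any AESI, which also pools hypersensitivity, anaphylaxis and a broad hepatic search, and Master SAP section 17 plans no statistical comparison of safety data. This stands too: removing COVID-19 terms from the pooled figure would not turn it into a bacterial-infection measure. Hence the proposal for separate rows with their own differences.

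Third, a broad infection category is a defensible conservative choice, since the absence of harm on coronavirus is an expectation and not a finding. That is a reason to keep the whole-class rows, not a reason to omit the narrower ones.

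Fourth, the rates are assumed, and antibiotic prophylaxis is required in both arms of this sub-protocol, which may lower bacterial events. Both points are fair. A reader might infer that the infection AESI is largely a count of COVID-19 worsening. The documents do not support that. They give no COVID-19 event rate, and progression recorded as respiratory failure would probably code elsewhere. The SAE definition in Appendix 4 also offers disease-related hospitalization and death as examples of what is not an SAE when the event is not an AE. That sits uneasily with 8.4.7, and the two should be reconciled.

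**Conclusion.** The point holds in a limited form. The Infections and Serious infections totals and the any-AESI risk difference can include COVID-19 worsening. In those aggregates a COVID-19 benefit could mask or reverse an excess of non-Neisseria bacterial infections.

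On the assumed rates, a benefit of roughly 3 to 5 points is enough to cancel a true +5-point bacterial excess in the whole-class row, and a benefit of 6.75 points can hide a rise of about 6 to 7 points. Without a COVID-19 benefit the dilution is modest: +3.0 to +4.25 of +5. In the any-AESI figure the effect is blended further with the other categories.

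This rests on four assumptions: the class in which COVID-19 terms are coded, site reporting under a COVID-19 diagnosis, independence of the two kinds of event, and the event rates themselves.

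A reader might go on to conclude that the report cannot answer the infection question at all. That does not follow, because the Neisseria rows, the preferred-term rows and the listing remain specific. What is missing is one aggregate count and its contrast. This is a cheap improvement to the safety summary, and it does not undermine the safety analysis.

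**What to change.** In COV-01-005 SAP 17.1.1:
- Keep the whole-class Infections and Serious infections rows.
- Add infections and serious infections excluding SARS-CoV-2/COVID-19 preferred terms, with the term list fixed before database lock. Give each its own risk difference and 95% CI.
- Show the COVID-19 terms as a separate row.
- Present the any-AESI risk difference both with and without COVID-19 terms, so that an adverse effect on COVID-19 is not lost from the summary.

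The cost is a short term list and a few table rows. A bacterial superinfection coded under a COVID-19 term would fall in the separate row, where it is still shown. The change removes a possible bias but adds no precision: with 108 patients, the interval half-width in the 5% vs 12% example is still about 10 to 13 points.
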